10.5 Concomitant Medications

Patients will be allowed to use any concomitant medications that they require except those listed in the exclusion criteria or protocol section 7.6. They may remain on HHT-directed medications other than those listed in the exclusion criteria if they were taking these when eligibility was determined. If they remain on such medications, they must remain on a stable dose during the study. Concomitant medications will be reviewed at screening, and at each study visit.

Incidence of taking HHT-directed medications and any exclusionary medications will be presented by treatment group, and include the following:

Excluded medications:

- octreotide,
- erythropoetic agents,
- oral estrogen or progestin
- bevacizumab (Avastin) (systemic or nasal)
- pazopanib
- ciprofloxacin
- fluvoxamine
- ketoconazole
- carbamazepine

Medications allowed to continue if on stable dose at screening but not allowed to initiate or increase dose:

- oral epsilon-aminocaproic acid (Amicar)
- oral tranexamic acid
- propranolol
- timolol
- epsilon aminocaproic acid
- tranexamic acid nasal sprays
- nasal estriol

11 REPORTING CONVENTIONS

Unless required otherwise by journal standards, the following rules are standard:

- Moment statistics including mean and standard deviation will be reported at 1 more significant digit than the precision of the data.
- Order statistics including median, min and max will be reported to the same level of precision as the original observations. If any values are calculated out to have more significant digits, then the value should be rounded so that it is the same level of precision as the original data.
- Following SAS rules, the median will be reported as the average of the two middle numbers if the dataset contains even numbers.
- Test statistics including t and z test statistics will be reported to two decimal places.
- P-value will be reported to 3 decimal places if > 0.001 . If it is less than 0.001 then report ' <0.001 '. Report p-values as 0.05 rather than .05.
- No preliminary rounding should be performed, rounding should only occur after analysis. To round, consider digit to right of last significant digit: if < 5 round down, if ≥ 5 round up.

12 CHANGES TO THE ANALYSES PLANNED IN THE PROTOCOL

The SAP expands the analysis of the primary and second endpoints described in the protocol. No changes from that specified in the protocol were made.

14 LIST OF POTENTIAL DISPLAYS

List of displays and table shells are in a separate document. Data displays (tables, figures, and listings) may be added, deleted, rearranged or the structure may be modified after finalization of the SAP. Such changes require no amendment to the SAP as long as the change does not contradict the text of the SAP.

15 APPENDIX 1 EPISTAXIS SEVERITY SCORE SCORING

The epistaxis severity score (ESS) was developed by Hoag et al and is a clinically-validated score for quantifying epistaxis in HHT which correlates inversely with QOL. Questions comprising the ESS are depicted in below.

Epistaxis Severity Score

Please answer each of the following questions as they pertain to your TYPICAL (usual or most common) symptoms during the past 4 weeks.

1. How often did you TYPICALLY have nose bleeding during the past 4 weeks?
 Less than monthly [0]
 Once per month [1]
 Once per week [2]
 Several per week [3]
 Once per day [4]
 Several per day [5]
2. How long did your nose bleeding episodes TYPICALLY last during the past 4 weeks?
 Less than 1 minute [0]
 1 to 5 minutes [1]
 6 to 15 minutes [2]
 16 to 30 minutes [3]
 More than 30 minutes [4]
3. How would you describe your TYPICAL nose bleeding intensity during the past 4 weeks?
 Not Typically Gushing or Pouring [0]
 Typically Gushing or Pouring [1]
4. Have you sought medical attention for your nose bleeding during the past 4 weeks?
 No [0]
 Yes [1]
5. Are you anemic (low blood counts) currently?
 No [0]
 Yes [1]
 I don't know [2]
6. Have you received a red blood cell transfusion SPECIFICALLY for nose bleeding during the past 4 weeks?
 No [0]
 Yes [1]

[figure not shown]
Clinical characteristics of the bleeding frequency and severity are collected and assigned a numerical score, which is added and multiplied by specific coefficients to determine the final ESS. The maximum ESS score is 10, with patients in the 7-10 range being considered to have severe epistaxis.

Calculations for determining the ESS are depicted below, and an automated determination of the ESS is programmed to be automatically calculated in the EDC system. The presence of missing data will result in no score being calculated.

Calculation of the Epistaxis Severity Score

Question	Response	Multiplied by		Coefficient	Result	
1	Less than monthly	0	X	0.14 (0.70 Den)		
	Once per month	1				
	Once per week	2				
	Several per week	3				
	Once per day	4				
	Several per day	5				
2	< 1 minute	0	X	0.25 (1.00 Den)		
	1-5 minutes	1				
	6-15 minutes	2				
	16-30 minutes	3				
	>30 minutes	4				
3	No	0	X	0.25 (0.25 Den)		
	Yes	1				
4	No	0	X	0.30 (0.30 Den)		
	Yes	1				
5	No	0	X	0.20 (0.20 Den)		
	Yes	1				
	I don't know	Drop		0		
6	No	0	X	0.31 (0.31 Den)		
	Yes	1				
Total				Denominator (Sum Den)	Raw Score	
Normalized HHT-EES				Raw Score	X 10	
= Raw Score / Denominator (2.76)						

16 APPENDIX 2 SCREEN SHOT OF EPISTAXIS DIARY

17 APPENDIX 2 INTERIM ANALYSIS AT 50%

The purpose of the 50% interim analysis is to assess for early efficacy of the primary efficacy outcome, the change from baseline in the ESS totals score at 24 weeks. Futility is not assessed at the 50% interim.

As stated in the protocol, the significance level of the primary outcome at the interim and final analysis will be based on Lan-DeMets α -spending functions with O'Brien-Fleming boundaries in order to maintain the study-wise α level at 0.05. The α level will be 0.0031 at 50%, 0.0183 at 75% and 0.0440 at the final analysis. The exact α level at the interim will be determined using Lan-DeMets α -spending functions based on the actual percent of data available at the interim.

The interim analysis will be reviewed by the DSMB at the meeting on October 19, 2022, based on data from a database snapshot date of **September 6, 2022**.

If the significance level of the primary outcome is less than the pre-specified alpha level, then the DSMB may recommend that study enrollment be halted, with currently active patients completing their treatment and follow-up, and the database be cleaned and locked for the final statistical analysis.

Study Population, Sample size and Alpha level

The interim efficacy analysis will be conducted on all randomized and treated participants (the modified Intent to Treat (MITT) population that will be used for the final statistical analysis as specified in the SAP) that have either completed the 24-week (C6) visit or have discontinued from the study. Participants that have completed C6 but have not yet completed the 4-week post-treatment follow-up are included.

Randomized participants that are ongoing in the trial and have not yet reached the C6 visit will not be included in the interim analysis. While their data collected as of the data snapshot is fully applicable, the repeated measures model used for the ESS 24-week analysis assumes that the data not yet collected for ongoing participants is missing at random and would be assumed to have a similar correlation with prior visits as participants that have complete data. While this assumption is to be evaluated for missing data in the final analysis (as specified in the SAP), we do not want to include cases with missing data that is yet to be collected in the interim analysis where a decision might be made about stopping the trial.

As of the database snapshot, there were **86** participants that met the criteria for inclusion in the interim efficacy analysis, which is **54%** of the total 159 planned sample size. Using Lan-DeMets α -spending functions with O'Brien-Fleming boundaries in order to maintain the study-wise α level at 0.05 based on the 2 planned interim analyses, the revised alpha level for the 54% initial interim is **0.0046**. The alpha level at the other 2 timepoints is now 0.0179 at 75% and 0.0439 at the final analysis.

Pooled Site

The statistical efficacy analysis adjusts for pooled site. For the interim analysis, sites with fewer than 10 participants will be pooled together with another site such that the new pooled site is not larger than the largest non-pooled single site. Sites with the smallest enrollment numbers will all be pooled together, and sites with moderately small numbers will be pooled with sites that are geographically similar.

The pooled sites for the interim analysis are as follows:

- Pooled small sites (n=14): Cleveland Clinic (n=4), Johns Hopkins (n=4), UCSF (n=2), Utah (n=4)
- Pooled moderately small sites (Midwest) (n=19): Wisconsin (n=7) pooled with Mayo (n=12)
- Non-pooled sites: MGH (n=28), UNC (n=15), Penn (n=10).

Tables and Figures

The efficacy interim analysis will be submitted to the DSMB with a full regular safety DSMB report. The safety DSMB report tables and figures include all available data for all randomized participants. Because this analysis population is different, a few DSMB displays will be repeated for the interim analysis using the interim analysis MITT population.

The following displays will be included in the interim efficacy analysis based on the interim analysis MITT population:

- CONSORT diagram
- Demographics table
- ESS table, showing change from baseline at each visit C1-C6, the average of C4, C5, and C6 and at the post-treatment follow-up visit. Model estimates, confidence intervals and p-values of the differences between treatment groups for the change from baseline at each timepoint will be provided. The model will be fitted based on the model provided in SAP Section 9.3. The primary p-value to be assessed for early study stopping (relative to the significance level of 0.0046) is the comparison between treatment groups at the c6 (week 24) visit. P-values for all other timepoints are purely descriptive.
- Table of the key secondary outcomes, showing descriptive statistics by treatment group but no statistical testing for the following:
 - Amount of parenteral iron administered (in mg) during the 24-week treatment period (pro-rated to 24 weeks in patients who discontinue early).
 - Amount of packed red blood cell transfusions (in units) during the 24-week treatment period (pro-rated to 24 weeks in patients who discontinue early).
 - Change in Neuro-QoL Satisfaction with Social Roles and Activities Short Form (V1.1) T-score from baseline to weeks 12 and 24 (key timepoint), and the post-treatment follow-up visit.
 - Change in the HHT-specific QOL total score from baseline to weeks 12 and 24 (key timepoint), and the post-treatment follow-up visit.
 - Change in average weekly epistaxis duration from the four-week screening period prior to baseline to weeks 8-12 and to weeks 20-24 (key timepoint), and to weeks 1-4 post-treatment.

18 APPENDIX 3 INTERIM ANALYSIS AT 75%

The purpose of the 75% interim analysis is to assess for both futility and early efficacy of the primary efficacy outcome, the change from baseline in the ESS totals score at 24 weeks.

As stated in the protocol, the significance level of the primary outcome at the interim and final analysis will be based on Lan-DeMets α -spending functions with O'Brien-Fleming boundaries in order to maintain the study-wise α level at 0.05. The α level will be 0.0031 at 50%, 0.0183 at 75% and 0.0440 at the final analysis. The exact α level at the interim will be determined using Lan-DeMets α -spending functions based on the actual percent of data available at the interim.

The interim analysis will be reviewed by the DSMB in June 2023, based on data from a database snapshot date of **May 30, 2023**.

If the significance level of the primary outcome is less than the pre-specified alpha level, then the DSMB may recommend that study enrollment be halted, with currently active patients completing their treatment and follow-up, and the database being cleaned and locked for the final statistical analysis.

Study Population, Sample size and Alpha level

The interim efficacy analysis will be conducted on all randomized and treated participants (the modified Intent to Treat (MITT) population that will be used for the final statistical analysis as specified in the SAP) that have either completed the 24-week (C6) visit or have discontinued from the study. Participants that have completed C6 but have not yet completed the 4-week post-treatment follow-up are included.

Randomized participants that are ongoing in the trial and have not yet reached the C6 visit will not be included in the interim analysis. While their data collected as of the data snapshot is fully applicable, the repeated measures model used for the ESS 24-week analysis assumes that the data not yet collected for ongoing participants is missing at random and would be assumed to have a similar correlation with prior visits as participants that have complete data. While this assumption about missing data is to be evaluated in the final analysis (as specified in the SAP), we do not want to include cases with missing data that are yet to be collected in the interim analysis where a decision might be made about stopping the trial.

As of the database snapshot, there were **127 participants** that met the criteria for inclusion in the interim efficacy analysis, which is **80%** of the total 159 planned sample size. Using Lan-DeMets α -spending functions with O'Brien-Fleming boundaries in order to maintain the study-wise α level at 0.05 based on the 2 planned interim analyses, the revised alpha level for the 54% initial interim was 0.0046, and the revised alpha level is now **0.0230 at 80% and 0.0425 at the final analysis**.

Futility

Futility for the primary efficacy outcome will be assessed by conditional power assuming the remaining outcome data to be collected will be similar to the data that has been collected thus far and not necessarily match the originally hypothesized difference. As stated in the protocol, the DSMB may recommend study stop due to futility if the upper limit of the 80% confidence interval for conditional power does not exceed 50%.

Conditional power will be calculated as follows:

$$ProbNorm \left\{ \left[\sqrt{\frac{(1-P)}{P}} + \sqrt{\frac{P}{(1-P)}} \right] Z - \frac{Z_\alpha}{\sqrt{1-P}} \right\}$$

where $Z = (\hat{T} / SE)$

- probnorm = the **lower** 1-sided alpha value corresponding to the Z value of the formula in the curly brackets based on a normal distribution with mean of zero and standard deviation of 1, denoted $N(0,1)$. We are using the lower tail because if the difference is calculated as placebo – pomalidomide, the Z will be negative if there is a treatment effect, corresponding to a greater decrease in the ESS score for pomalidomide than placebo
- p= the percentage of data available at the interim analysis (**=0.80**)
- Z_α = critical value for the one-sided alpha at the end of the study (**= -2.0286**, corresponding to Z for alpha = **0.0425/2**). If the difference is placebo – pomalidomide, the Z will be negative, corresponding to a greater decrease in the ESS score for pomalidomide than placebo
- \hat{T} is the estimate of the treatment group difference (placebo-pomalidomide) from the MMRM model at C6
- SE is the standard error of the estimate of the treatment group difference from the MMRM model at C6

The 80% confidence interval for the conditional power is calculated as:

$$ProbNorm \left\{ \sqrt{\frac{(1-P)}{P}} \times (Z \pm Z_\gamma) + \sqrt{\frac{P}{(1-P)}} \times Z - \frac{Z_\alpha}{\sqrt{1-P}} \right\}$$

Where Z_γ is the Z value corresponding to the lower 1-sided tail of the $N(0,1)$ distribution at the alpha level = $(1-0.8)/2 = 0.10 = -1.28155$

Pooled Site

The statistical efficacy analysis adjusts for pooled site. For the interim analysis, sites with fewer than 10 participants will be pooled together with another site such that the new pooled site is not larger than the largest non-pooled single site. Sites with the smallest enrollment numbers will all be pooled together, and sites with moderately small numbers will be pooled with sites that are geographically similar.

The pooled sites for the interim analysis are as follows:

- Pooled small sites (n=21): Cleveland Clinic (n=6), Johns Hopkins (n=6), UCSF (n=2), Utah (n=6), and UCSD (n=1)
- Non-pooled sites: MGH (n=43), UNC (n=20), Penn (n=15), Wisconsin (n=11), Mayo (n=17)

Tables and Figures

The efficacy interim analysis will be submitted to the DSMB with a full regular safety DSMB report. The safety DSMB report tables and figures include all available data for all randomized participants. Because this analysis population is different, a few DSMB displays will be repeated for the interim analysis using the interim analysis MITT population.

The following displays will be included in the interim efficacy analysis based on the interim analysis MITT population:

- CONSORT diagram
- Demographics table
- ESS table, showing change from baseline at each visit C1-C6, the average of C4, C5, and C6 and at the post-treatment follow-up visit. Model estimates, confidence intervals and p-values of the differences between treatment groups for the change from baseline at each timepoint will be provided. In addition, the conditional power and corresponding 80% confidence interval will be provided for the C6 timepoint. The model will be fitted based on the model provided in SAP Section 9.3.
 - The primary p-value to be assessed for early study stopping for efficacy (relative to the significance level of **0.0230**) is the comparison between treatment groups at the C6 (week 24) visit. P-values for all other timepoints are purely descriptive.
 - Stopping early for futility will be assessed using the upper bound of the 80% confidence interval for conditional power at the C6 (week 24) visit (relative to the outpoint level of 50%).
- Table of the key secondary outcomes, showing descriptive statistics by treatment group but no statistical testing for the following:
 - Amount of parenteral iron administered (in mg) during the 24-week treatment period (pro-rated to 24 weeks in patients who discontinue early).
 - Amount of packed red blood cell transfusions (in units) during the 24-week treatment period (pro-rated to 24 weeks in patients who discontinue early).
 - Change in Neuro-QoL Satisfaction with Social Roles and Activities Short Form (V1.1) T-score from baseline to weeks 12 and 24 (key timepoint), and the post-treatment follow-up visit.
 - Change in the HHT-specific QOL total score from baseline to weeks 12 and 24 (key timepoint), and the post-treatment follow-up visit.
 - Change in average weekly epistaxis duration from the four-week screening period prior to baseline to weeks 8-12 and to weeks 20-24 (key timepoint), and to weeks 1-4 post-treatment.

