**Analysis Method:** We conservatively conduct initial sample size calculations based on a T-test with equal variances (using the Power procedure within SAS). Since the primary analysis is an MMRM model with adjustment for baseline score, we next perform sensitivity power calculations which account for expected improvement in power based on the analysis plan. Data provided from the NOSE study indicated that the correlation between baseline and change from baseline at post-baseline visits is likely to be -0.4, and correlation between post-baseline visits is likely to be 0.5. Adjustment for baseline would reduce the standard deviation of the residual from 1.7 to 1.6. To evaluate power of the MMRM model in the face of increasing percent of missing data across study visits, we compute power using the formula by Lu, Luo, and Chen.

**Calculation and Sensitivity Analysis:** A total sample size of 159 patients (106 pomalidomide, 53 placebo) will provide 90% power to identify a treatment group difference in ESS change from baseline at 24 weeks of 1.0 with  $p<0.044$ , assuming a standard deviation of 1.7 and 10% early discontinuation rate. Power will remain above 80% if there is a substantially higher than expected study discontinuation rate of 30% (with 10% providing no post-baseline data): 81% based on a conservative

T-test, or 90% with the planned MMRM analysis. If the standard deviation is 1.8 instead of 1.7, the power for the planned MMRM analysis would be 91% with 10% discontinuation, and 87% with 30% discontinuation. Table 7 provides calculations for sample size selection, and Table 8 provides sensitivity of the power for the selected sample size.

Pomalidomide vs placebo Mean difference in ESS change from BL at W24	Std Dev of ESS change from BL at W24	Effect size = (mean difference) /SD	Power	Planned sample size with post-baseline data	Planned study early D/C rate	Total sample size.
-1.0	1.9	0.526	90%	180 (120:60)	10%	198 (132:66)
-1.0	1.8	0.556	90%	162 (108:54)	10%	178 (119:59)
-1.0	1.7	0.588	90%	144 (96:48)	10%	159 (106:53)
-1.0	1.6	0.625	90%	129 (86:43)	10%	141 (94:47)
-1.2	1.7	0.706	97%	144 (96:48)	10%	159 (106:53)
-0.7	1.7	0.412	62%	144 (96:48)	10%	159 (106:53)

Note: In each row, the bolded number was calculated. All other items in the row were fixed. Calculations based on a 2-sample T-test

**Table 7.** Sample size calculations for 2:1 randomization and Alpha = 0.044.

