Calculation Method	Std Dev	Planned study early D/C rate	Power
T-test	1.7	10%	90%
MMRM*	1.7	10%	94%
T-test	1.7	20%	87%
MMRM*	1.7	20%	92%
T-test	1.7	30%	81%
MMRM*	1.7	30%	90%
T-test	1.8	10%	87%
MMRM*	1.8	10%	91%
T-test	1.8	20%	83%
MMRM*	1.8	20%	89%
T-test	1.8	30%	76%
MMRM*	1.8	30%	87%

Note: MMRM includes adjustment for baseline assuming a correlation of -0.4 between baseline and change from baseline, and assumes 10% have no post-baseline data, and half of the remaining drop-outs occur between the first and second post-baseline visits.

**Table 8.** Power Sensitivity Analysis for N=159, Mean Difference=-1.0 and Alpha = 0.044.

With 159 patients, we will also have at least 90% power to identify a treatment group difference of 30% for a binary secondary endpoint of proportion of participants requiring at least one packed red blood cell transfusion or iron infusion at any time during the 24-week treatment period with  $p < 0.05$ , whether assuming a rate in the placebo and pomalidomide groups of 90% and 60%, or 50% and 20%, as demonstrated in Table 9.

Total sample size.	Planned discontinuation rate	Planned sample size (completers)	Power for selected proportions (Pomalidomide vs placebo)	
			60% vs 90%	20% vs 50%
159 (106:53)	10%	144 (96:48)	98%	96%
159 (106:53)	20%	126 (84:42)	97%	93%
159 (106:53)	30%	111 (74:37)	94%	90%

**Table 9.** Power for comparison of treatment groups for proportion of patients with at least one packed red blood cell transfusion or iron infusion during the treatment period for 2:1 randomization with Alpha = 0.05.

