9.2 Efficacy Variables

Primary and secondary efficacy variables as well as exploratory and safety outcomes are described in the table below.

Variable	Type	Definition
Primary Outcome		
Change from baseline in Epistaxis Severity Score at each post-baseline visit through 24 weeks and 4 weeks post-treatment	Continuous	
The Epistaxis Severity Score will be computed at baseline and at each study visit during which assessments are administered and collected using the standard scoring algorithm (see Appendix 1). The outcome will then be computed as the difference in score at each visit and the score at baseline. If data at a time point for the assessment are missing, the outcome variable will be coded as missing. The total score be calculated inside the EDC CRF page.

Key Secondary Outcomes		
Amount of iron administered through 24 weeks and 4 weeks post-treatment	Continuous	
The 4-week average amount of iron transfusion (in mg/4 weeks) through 24 weeks will be calculated. For subjects who discontinue early, this value will be pro-rated to 24 weeks. Participants who receive no infusions during the 24 weeks will have a value of zero,
 
In the screening period, the amount of iron received in the 6 months prior to screening is calculated as the number of infusions received multiplied by the amount infused at the last infusion (because the CRF only collected the amount infused at the most recent infusion prior to screening)

Amount of red blood cell administered through 24 weeks and 4 weeks post-treatment This was changed to: proportion of patients receiving at least 1 blood transfusion in the 24-week period.	Continuous Categorical (yes/no)	
The 4-week average amount of red blood cell transfusion (in units/4-weeks) through 24 weeks will be calculated. For subjects who discontinue early, this vale will be pro-rated to 24 weeks.
 
Note: at masked data review, it was determined the overall number of RBC transfusions was small, and this outcome will instead be modified to the percentage of participants that received any RBC transfusion during the 24-week treatment period (and separately, the 4-week post-treatment period)

Change from baseline in Neuro-QoL™ Satisfaction with Social Roles and Activities Short Form (V1.1) T-score	Continuous	The Neuro-QoL™ Satisfaction with Social Roles and Activities Short Form (V1.1) T-score will be computed at baseline and at each study visit during which assessments are administered and collected. Total score

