9.6 Formal Interim Efficacy Analysis

We will perform a formal interim analysis to evaluate for early overwhelming efficacy based on the change in ESS score from baseline to 24 weeks after 50% and 75% of subjects have completed the 24-week visit or discontinued the study. Futility will also be assessed at 75%, and each formal interim analysis will include a full DSMB safety review.

For assessing early efficacy, the significance level for the interim and final analysis will be based on Lan-DeMets α -spending functions with O'Brien-Fleming boundaries in order to maintain the study-wise α level at 0.05. The α level will be 0.0031 at 50%, 0.0183 at 75% and 0.0440 at the final analysis. The exact α level at the interim will be determined using Lan-DeMets α -spending functions based on the actual percent of data available at the interim.

Assuming 90% power at the end of the study, there is a 26% chance of meeting the stopping boundary at the 50% interim, and a 69% chance at the second interim. If the study actually has 80% power (for example, due to higher-than-expected discontinuation rate or ESS standard deviation), then there is a 54% chance of meeting the stopping boundary at the second interim. Conversely, if the study actually has power $> 95\%$ (for example if treatment group difference in ESS change is 1.2 rather than 1.0 or lower than expected standard deviation), then the chance of stopping is 41% at the first interim and 84% at the second interim.

Futility will be assessed at 75% based on conditional power of the primary efficacy variable. The DSMB may recommend study stop due to futility if the upper limit of the 80% confidence interval for conditional power does not exceed 50%.

With our planned enrollment rate, we expect approximately 6 months of randomization visits to take place after the 50% interim analysis, and so there is a potential to decrease the overall study sample size in the event that the DSMB recommends stopping enrollment based on the interim analysis results. If enrollment proceeds as planned, then randomization will be essentially complete by the time of the 75% interim analysis. In this case, we will request the DSMB to skip the second interim analysis in order to maximize the alpha level at the end of the study. Otherwise, if enrollment is slower than expected, then the results of the second interim analysis still provide a chance to decrease the study sample size.

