Both interim analyses were carried out. Details are provided in **Appendix 2** and **Appendix 3**.

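### The futility formula in SAP Appendix 3 has inconsistent signs, so as printed it does not return conditional power under either reading of Z

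*SAP*

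**What the plan says.** SAP section 9.6 sets the rule: "The DSMB may recommend study stop due to futility if the upper limit of the 80% confidence interval for conditional power does not exceed 50" per cent. Appendix 3 (Interim Analysis at 75%) supplies the formula and, under Tables and Figures, makes its upper limit the decision quantity: "Stopping early for futility will be assessed using the upper bound of the 80% confidence interval for conditional power" at the C6 visit.

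The formula in Appendix 3 is

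ProbNorm{ [√((1-P)/P) + √(P/(1-P))]·Z - Zα/√(1-P) }, with Z = T̂/SE.

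The 80% limits add ±Zγ inside the first term. The definitions given with it are:

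- ProbNorm is the lower tail.
- P = 0.80.
- Zα = -2.0286, for a final two-sided alpha of 0.0425.
- Zγ = -1.28155.
- T̂ "is the estimate of the treatment group difference (placebo-pomalidomide) from the MMRM model at C6".
- On direction, "the Z will be negative if there is a treatment effect, corresponding to a greater decrease in the ESS score for pomalidomide than placebo". The entry for Zα repeats this claim.

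Elsewhere the documents fix the direction of benefit. In Protocol section 10.5, Table 7 has a column headed "Pomalidomide vs placebo Mean difference in ESS change from BL at W24" with -1.0 as the planning value, and Table 8 is captioned "Power Sensitivity Analysis for N=159, Mean Difference=-1.0 and Alpha = 0.044". In SAP section 9.2, the time-to-response outcome counts a difference from baseline of -1.0 or lower as the improvement.

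**The concern.** There are two separate faults.

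1. **Sign of Z.** If pomalidomide minus placebo is -1.0 under the design effect, placebo minus pomalidomide is +1.0. Z is then positive when the drug works, not negative as Appendix 3 says twice.
2. **Sign and tail do not match.** Suppose one accepts that Z is negative for benefit. A negative Z with a negative critical value needs the upper tail of this expression, but the SAP specifies the lower. If instead Z is positive for benefit, the lower tail is right but the critical value must be +2.0286.

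This is the only numerical futility criterion in the plan. Followed as written, it would show the DSMB a conditional power near 100% for a null result. Under one reading it would also label a strongly favourable result as futile.

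**Working it through.** **Reproducing the SAP's own constants.** The lower 0.0425/2 normal quantile is -2.0286 and the lower 0.10 quantile is -1.28155; both match. Lan-DeMets O'Brien-Fleming spending at 54%, 80% and 100% gives 0.0046, 0.0230 and 0.0425, also matching. The magnitudes are right; only the signs are at issue.

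**Reference formula.** Let z be the interim statistic, positive for benefit. Under the current trend, which Appendix 3 says it assumes, the final statistic has mean z√P + (1-P)z/√P and variance 1-P. Hence

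CP = Φ{ [√((1-P)/P) + √(P/(1-P))]·z - 2.0286/√(1-P) }.

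At P = 0.80:

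- Bracket: 0.5 + 2.0 = 2.5.
- Critical-value term: 2.0286/√0.2 = 4.536.
- Half-width term: 0.5 × 1.28155 = 0.641.

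So CP = Φ(2.5z - 4.536), with upper 80% limit Φ(2.5z - 3.895). Simulating the final statistic given the interim z (1,000,000 draws) gives 0.216 at z = 1.5 and 0.957 at z = 2.5, agreeing with the formula.

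**Printed formula.** Substituting Zα = -2.0286 turns the last term into +4.536. The result is Φ(2.5Z + 4.536), with upper limit Φ(2.5Z + 5.177).

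- Reading A, Z negative for benefit (as the text says): Φ(-2.5z + 4.536) = 1 - CP exactly.
- Reading B, Z computed literally as placebo minus pomalidomide: Φ(2.5z + 4.536).

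| Benefit z | CP (upper limit) | Reading A (upper limit) | Reading B |
|---|---|---|---|
| 0 | 0.0% (0.0%) | 100.0% (100.0%) | 100.0% |
| 1.0 | 2.1% (8.1%) | 97.9% (99.6%) | 100.0% |
| 1.5 | 21.6% (44.2%) | 78.4% (92.3%) | 100.0% |
| 2.0 | 67.9% (86.5%) | 32.1% (57.0%) | 100.0% |
| 2.5 | 95.7% (99.1%) | 4.3% (14.2%) | 100.0% |

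**When the rule is met** (upper limit no more than 50%):

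- Consistent signs: z ≤ (4.536 - 0.641)/2.5 = 1.56.
- Reading A: z ≥ (4.536 + 0.641)/2.5 = 2.07.
- Reading B: z ≤ -2.07.
- For comparison, the efficacy boundary at 0.0230 is z = 2.273.

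**Null trials flagged** (interim z standard normal): Φ(1.558) = 94% with consistent signs. The figure is 1.9% under Reading A and 1.9% under Reading B.

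**Trials at the design effect.** The interim mean z must be assumed.

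- SD 1.7, 127 participants at 2:1, difference 1.0: SE = 1.7·√(3/127 + 1.5/127) = 0.320, so mean z = 3.12.
- The same with 10% lacking C6 data: SE = 0.337, mean z = 2.96.
- Working back from 90% final power: (2.0286 + 1.2816)·√0.8 = 2.96.

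Over 2.96 to 3.12, consistent signs flag 6 to 8% of trials and Reading B essentially none. Reading A flags 81 to 85%. Of these, 75 to 80 percentage points also cross the efficacy boundary and 5 to 6 do not.

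**On the ESS scale** (SD 1.7; in brackets with 10% lacking C6 data), consistent signs flag an observed benefit of 0.50 (0.53) or less. Reading A flags a benefit of 0.66 (0.70) or more.

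**The case against.** The strongest reply is that the expression itself is the standard current-trend formula. With T̂ as defined and the lower tail, it becomes correct once the critical value is +2.0286. On that view this is an erratum in one sign and two explanatory sentences. That describes the repair fairly, but a program written to the printed definitions would still not return conditional power.

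The practical stakes are also limited:

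- The rule says only that the DSMB may recommend stopping.
- The C6 estimate, confidence interval and p-value sit in the same table. A conditional power near 100% beside a z near zero, or a futility flag beside a crossed efficacy boundary, should be noticed.
- The look already held 127 participants. The pre-lock site counts in SAP section 7.6 sum to 24 + 51 + 21 + 16 + 12 + 21 = 145, so a missed flag concerned few further patients.
- SAP section 9.6 records that "Both interim analyses were carried out", so the rule has no further prospective use. The program may have been right.

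All of this stands. It limits the consequence without making the printed rule correct.

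Two technical points also have merit. First, Z comes from a baseline-adjusted MMRM, so the residual SD of 1.6 in Protocol section 10.5 or the 94% power in SAP section 6 could replace the inputs used here. With 94% power the interim mean z is (2.0286 + 1.5548)·√0.8 = 3.21; consistent signs then flag 5% and Reading A 87%. With SD 1.6 and 127 participants the ESS thresholds are 0.47 and 0.62. These shifts are modest, and the z thresholds and null rates do not depend on them. Second, the general definition of ESS change, "The outcome will then be computed as the difference in score at each visit and the score at baseline", does not by itself fix the order of subtraction. The direction rests on Protocol Tables 7 and 8 and the -1.0 response threshold in SAP section 9.2.

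A PDF reading error is an unlikely explanation: the minus sign before Zα appears in both formulas, and the lower tail and the sign claim are also stated in words.

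**Conclusion.** The concern holds: the futility rule is wrong as written. With the lower tail and Zα = -2.0286, neither sign of Z yields conditional power, the 80% limits inherit the error, and nothing elsewhere in the SAP or protocol corrects it. The main fault is that a null result appears near 100% and is almost never flagged. Reading A also inverts the rule for favourable results, though mostly where the efficacy boundary would be crossed at the same look.

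The table, the z thresholds and the null flag rates rest only on the SAP's constants and the usual normal approximation. The design-effect percentages and ESS thresholds depend on the assumed SD, power and missing data. Efficacy boundaries, type I error and the final alpha of 0.0425 are untouched. The effect on the June 2023 review is unknown, because the documents show neither the program nor the value reported. This should be fixed, but it does not threaten the final analysis.

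**What to change.** Issue a dated correction to SAP Appendix 3 with one consistent convention. Either of these works, and they are equivalent:

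- Z = (placebo - pomalidomide)/SE, positive for benefit, with Zα = +2.0286 and the lower tail.
- Z = (pomalidomide - placebo)/SE, negative for benefit, with Zα = -2.0286, reporting 1 - ProbNorm.

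Correct both statements about the sign of placebo minus pomalidomide. Zγ can stay, because it enters as plus or minus.

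Then check which signs the interim program used, recompute conditional power and its 80% limits from the May 30, 2023 snapshot, and record which values the DSMB received.

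The cost is one document correction, one program check and one recalculation on existing data. It needs no patients and no change to the final analysis.
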